Therefore, if our study is successful in implementing a sustainable evidence-based dietary program, the next step will be to establish a specialized nutritional prenatal care service designed to prevent clinical complications and improve pregnancy outcomes. This will involve

increasing the dedicated time and frequency of comprehensive dietary counseling sessions during gestation. These sessions will be independent from routine prenatal care visits. In addition, we plan to work with local government and private healthy diet organizations to help socially vulnerable pregnant women overcome nutritional challenges.

Objectives and Hypothesis

Primary Objective

To examine the feasibility and adherence to a MedDiet program initiated in the first or early second trimester of gestation (6-16 weeks) among overweight and obese women.

Hypothesis: Overweight and obese pregnant women enrolled in the MedDiet program have an elevated level of adherence facilitated by the design of a comprehensive dietary program with free home-delivered meals, nuts, and EVOO bottles. This hypothesis will be tested by examining adherence to the MedDiet program using a validated screening tool.³⁹

Secondary Objectives

1. To estimate the preliminary efficacy of a MedDiet intervention controlling gestational weight gain and reducing adverse pregnancy outcomes (APO).

Hypothesis: Overweight or obese pregnant women consuming MedDiet have low rates of excessive gestational weight gain and adverse pregnancy outcomes. This hypothesis will be tested by comparing gestational weight gain and pre-selected pregnancy outcomes between women allocated in each dietary group.

2. To estimate the preliminary impact of MedDiet intervention on maternal cardiometabolic profile.

Hypothesis: MedDiet leads to favorable effects on cardiovascular clinical parameters and cardiometabolic biomarkers in pregnancy. This hypothesis will be tested by comparing maternal cardiovascular parameters trends and cardiometabolic biomarkers during pregnancy among the studied groups.

Methods and Measures

Study Design

Type of study

This is a prospective, randomized, pilot study with a behavioral intervention. Sixty participants diagnosed as overweight ($BMI 25.0-29.9 \text{ kg/m}^2$) or obese ($BMI \geq 30.0 \text{ kg/m}^2$) in the first or early second trimester of gestation will be invited to participate.

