- **Cardiovascular parameters:** MedDiet is associated with reduction of blood pressure (BP) in non-pregnant adult overweight or obese women.⁵² Physiological changes of blood pressure (BP) during pregnancy are characterized by reduction of BP in the second trimester with return to the pre-pregnancy level late in the third trimester and postpartum period.⁵³ Heart rate (HR) increases by 20% to 25% over baseline during gestation.⁵⁴ Maternal BP and HR will be obtained by a calibrated automated oscillometric device during prenatal visits from the first to the third trimesters following the standardized technique established in our clinic. Trends of BP and HR throughout gestation will be compared among women allocated in the intervention and the control groups.
- **Cardiometabolic biomarkers:** Consumption of MedDiet is associated with lower levels of total cholesterol,⁵³ reduces insulin resistance preventing type 2 diabetes^{30,31} and GDM,^{34,36} and reduces markers of subclinical inflammation such as C-reactive protein (CRP).⁵⁵ Pregnancy is characterized by increased levels of total cholesterol, low-density lipoprotein (LDL), high-density lipoprotein (HDL), and triglycerides, especially in the second and third trimester,⁵⁶ and pregnancy is a state of increased insulin resistance.⁵⁷ There is limited knowledge about the effect of MedDiet on cardiometabolic biomarkers during pregnancy. Maternal lipid profile, random glucose level, hemoglobin A1C, and CRP levels will be compared at baseline (6-16

weeks) and at 26-30 weeks of gestation among participants in the intervention and the control groups. The labs will be obtained at the same time of scheduled blood draws for routine prenatal labs.

Analytical Plan

This is prospective randomized pilot study of sixty participants who will be randomly allocated in the MedDiet group or in the control group. Because this is a pilot study, a sample size was not calculated. Results will be analyzed initially using descriptive statistics. Comparison between groups will be done using chi square tests for proportions, and t-tests or ANOVA procedures for continuous variables. Regression analysis will be performed to identify independent outcome predictors. Other inferential statistical analysis will be conducted as appropriate.

Human Subjects Protection

Screening and Recruitment

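### Secondary objective 1 is to estimate efficacy on adverse pregnancy outcomes, but the Analytical Plan names no between-arm effect measure or interval, only chi-square tests, with about 1 to 4 events per arm expected for three of the outcomes

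*Combined protocol and SAP*

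**What the plan says.** In the combined protocol and SAP, under Secondary Objectives, the first objective is "To estimate the preliminary efficacy of a MedDiet intervention controlling gestational weight gain and reducing adverse pregnancy outcomes (APO"). Its hypothesis is handled as follows: "This hypothesis will be tested by comparing gestational weight gain and pre-selected pregnancy outcomes between women allocated in each dietary group"

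The Analytical Plan says that no sample size was calculated because this is a pilot. It then gives four sentences of method:

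- The first step is summary: "Results will be analyzed initially using descriptive statistics"
- The arms are then compared by test: "Comparison between groups will be done using chi square tests for proportions, and t-tests or ANOVA procedures for continuous variables"
- Next comes modelling, with no outcome named: "Regression analysis will be performed to identify independent outcome predictors"
- The last sentence is a catch-all: "Other inferential statistical analysis will be conducted as appropriate"

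For cardiovascular parameters, the Outcomes section adds: "Trends of BP and HR throughout gestation will be compared among women allocated in the intervention and the control groups"

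No risk difference, risk ratio, odds ratio, mean difference or confidence interval appears anywhere in the text supplied. The APO table under Outcomes lists five outcomes with background prevalences but no effect measure.

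**The concern.** An estimation objective calls for an estimate and a statement of its precision. The plan commits to a test instead and leaves everything else open.

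For the rarer APOs the committed p-value would be close to empty. A non-significant result is the likely outcome whether the diet does nothing or a great deal, and it could later be read as no effect. The protocol's introduction says that the study will supply preliminary efficacy data as a foundation for larger trials on pregnancy and neonatal outcomes, so later readers need the size of the difference and its uncertainty.

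The regression sentence names no outcomes. It therefore leaves room for predictor models on outcomes with only a handful of events.

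**Working it through.** **Inputs.** 60 participants, 30 per arm (Sample Size). Background rates are from the APO table under Outcomes. The plan states no significance level, continuity correction or dropout rate. I assume a two-sided 0.05 level, an uncorrected Pearson chi-square and no dropout; dropout would lower every count. The plan has no event or power figure to reproduce.

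**Step 1: expected events.** Per arm = 30 × p; both arms at equal risk = 60 × p.

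| Outcome | Rate p | Per arm | Both arms |
|---|---|---|---|
| HDP | 4–6% | 1.2–1.8 | 2.4–3.6 |
| HDP, BMI ≥40 rate | 12% | 3.6 | 7.2 |
| GDM | 6–14% | 1.8–4.2 | 3.6–8.4 |
| Preterm birth | 10.2% | 3.06 | 6.12 |
| Cesarean | 29.9% | 8.97 | 17.94 |

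The 4–6% HDP rate is labelled for BMI ≥30, while the trial enrols from BMI 25. The preterm rate is for the general US population, and the table says that risk is higher in overweight and obese women. Preterm birth would exceed 4 per arm only at a rate above 4/30 = 13.3%. Large for gestational age has no stated rate.

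**Step 2: what the chi-square can show.** With a and b events among 30 and 30, and p̄ = (a+b)/60, X² = ((a−b)/30)² / [p̄(1−p̄) × 2/30].

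Suppose the diet prevents every HDP case, so the MedDiet arm has 0 events:

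- 0 vs 3: 0.0100 / (0.05 × 0.95 × 0.0667) = 3.16, p = 0.076
- 0 vs 4: 0.0178 / (0.0667 × 0.9333 × 0.0667) = 4.29, p = 0.038

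Rejection therefore needs at least 4 control events:

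- At 4%: 1 − (0.294 + 0.367 + 0.222 + 0.086) = 0.031
- At 6%: 1 − (0.156 + 0.299 + 0.277 + 0.165) = 0.103

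Enumerating all 31 × 31 tables gives these rejection rates (the halving is my assumption):

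| Outcome | No effect | Risk halved | All cases prevented |
|---|---|---|---|
| HDP 4–6% | 1.9–3.7% | 1.8–4.6% | 3.1–10.3% |
| HDP 12% | 5.5% | 12.9% | 49% |
| GDM 6–14% | 3.7–5.4% | 4.6–14.9% | 10–62% |
| Preterm birth 10.2% | 5.5% | 10.8% | 37% |
| Cesarean 29.9% | 4.9% | 28% | 99% |

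**Step 3: what an interval adds.** For 1/30 vs 3/30 the chi-square gives p = 0.30. The risk difference is −6.7 points, Newcombe 95% interval −22.5 to +8.2, which shows that neither benefit nor harm is excluded. For 3/30 vs 3/30 it is 0 points (−16.9 to +16.9).

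**Step 4: the interval method must be fixed.** For 0/30 vs 4/30, Newcombe gives −29.7 to +0.6 points and Miettinen-Nurminen about −30 to −1. One includes zero and the other does not.

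**Step 5: regression.** At 2.4 to 8.4 events in total, even a model with only arm and BMI category has 2.4/2 = 1.2 to 8.4/2 = 4.2 events per coefficient.

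**Step 6: continuous outcomes.** Randomization and Study Groups balances on BMI category, and the weight-gain targets differ by that category (15–25 lb against 11–20 lb). Starting weight, early blood pressure and heart rate, and biomarkers at 6–16 weeks are collected. A plain t-test uses none of this and by itself gives no interval.

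**The case against.** The strongest reply has four parts.

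1. **The protocol says that the hypothesis will be tested by comparison, so a test fits its wording.** True, but the objective itself is worded as estimation, and a test alone does not deliver that.
2. **Descriptive statistics will give percentages by arm, and the catch-all sentence permits an interval.** This largely stands: the difference is one subtraction away. Permission is not a commitment, though, and the choice of measure and method is left until results are seen.
3. **This is a pilot and low power is disclosed.** This stands in full. Lack of power is not the complaint; the rejection rates only show how little the p-value conveys.
4. **Nothing says that sparse outcomes will be modelled.** Also true. The regression sentence does not exclude it, and that is all that can be said.

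A reader might infer that the chi-square test is invalid because expected event cells fall below 5. The figures do not support that. Its false-positive rate is 1.9–5.5% at the rates for the three sparse outcomes, and at most about 5.5% over event rates of 1–50%. Nor does disagreement with Fisher's exact test (0 vs 4: 0.038 against 0.112) show that the chi-square is wrong, because Fisher's own false-positive rate here is only 0.06–1.6%. The plan does not say whether a continuity correction applies; with Yates, the same table gives p = 0.12.

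**Conclusion.** The point holds as a mismatch between objective and analysis. The stated aim is to estimate efficacy on APOs, and no between-arm measure or interval is pre-specified. For HDP, GDM and preterm birth, with 1.2 to 4.2 expected events per arm, the committed p-value carries little information: rejection rates of about 2–15% if risk is halved, and 3–10% for HDP at 4–6% even if every case is prevented.

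The description is strongest for HDP and weaker at the top GDM rate, where complete prevention would be detected 62% of the time. It does not extend to cesarean delivery, which is not sparse, and cannot be judged for large for gestational age.

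The size rests on the protocol's background rates, full retention, an uncorrected test and a 0.05 level; the last three are my assumptions. This is a secondary, preliminary objective in a feasibility pilot, so the change is worth making but does not threaten the trial.

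**What to change.** Amend the Analytical Plan in three places.

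1. **APOs.** For each of the five outcomes, report counts and percentages by randomised arm and the risk difference (MedDiet minus control) with a 95% confidence interval from one method named now, for example Newcombe. Do not list Newcombe and Miettinen-Nurminen as alternatives. State that no conclusion of efficacy, or of no effect, will rest on an APO p-value.
2. **Regression.** Name the outcomes for which predictors will be sought and limit them to those that can support a model. Do not fit predictor models to HDP, GDM or preterm birth.
3. **Continuous outcomes.** For gestational weight gain, blood pressure, heart rate and biomarkers, replace the unadjusted t-test with the between-arm difference and its 95% confidence interval, adjusted for BMI category and for the baseline value where collected.

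The cost is wording: no new data, visits or participants. The intervals will be wide and will not size a later trial, and there will be no predictor tables for the sparse outcomes.
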